[name], Back in Motion Physiotherapy Clinic, Dunedin

Email: [contact]

[name], Centre for Health, Activity and Rehabilitation Research (CHARR), School of Physiotherapy, University of Otago

Email: [contact]

[name], Centre for Health, Activity and Rehabilitation Research (CHARR), School of Physiotherapy, University of Otago

Email: [contact]

[name], Centre for Health, Activity and Rehabilitation Research (CHARR), School of Physiotherapy, University of Otago

Email: [contact]

Background

Concussion or mild Traumatic brain injury is a heterogeneous injury resulting in a diverse range of impairments to both the neurological and musculoskeletal structures of the head-neck complex [1]. Of those sustaining a concussion, as many as 30% go on to experience persistent post-concussion symptoms (PPCS) [2]. The strongest predictor for development of PPCS is acute symptom load [3] Consequently, primary outcomes selected in clinical trials often reflect current understanding that symptom amelioration is an indicator of clinical recovery [4]. This being so, it is reasonable to conclude that optimal acute concussion management would contribute to earlier reduction in symptom load.

To address the heterogeneity of injury phenotypes, multidisciplinary assessment and management is advised [1]. So far, preliminary evidence suggests that treatment of specific domains is effective. However, such results are usually only found in studies where participants are selected based on a comprehensive screening process, and those with impairments specific to the treatment proposed by the study are eligible to participate [5, 6]. Studies which have not identified participants this way have failed to demonstrate treatment effect when interventions to address an injury phenotype was applied [4]. These results

suggest that while treatment to address specific injury phenotypes may be beneficial, implementation of an optimal patient pathways to the most appropriate treatment for individuals post-concussion is not always straight forward.

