1. To examine feasibility of implementing a simplified physical examination (SPE) aimed at identifying patients suited to cervical spine OMT and neuromuscular/ sensorimotor retraining, within a New Zealand Primary Health Care setting.
2. Based on response to treatment over time, to provide preliminary evidence regarding the

efficacy of the simplified physical examination to accurately identify individuals who may be suited to physiotherapeutic intervention consisting of OMT and neuromuscular/sensorimotor retraining. Included in this objective will be use of data to validate a clinical objective oculomotor screen to improve clinical utility of the SPE.

We hypothesise that using the SPE will aid in identification of individuals suited to orthopedic manual therapy of the neck. Consequently, primary outcomes including clinician attitude toward using the SPE in a primary health care setting, and participant compliance and satisfaction with the OMT intervention will be positive. Further we anticipate that measurable improvement (objectively assessed neck function and clinical presentation) in response to the selection to neck OMT based on the SPE will be observable over time. Results will therefore support feasibility of using the SPE for acute patient assessment, as well as the clinical efficacy of this approach for managing neck related signs and symptoms following concussion.

Methods

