Study Design: This is a mixed methods feasibility study consisting of 3 parts and will investigate clinician and patient response to a ***simplified physical examination (SPE)*** used to inform post-concussion management. Part 1 (Experimental Study a.), a single-group pretest-posttest clinical design will provide preliminary (pilot) evidence of combined effect of assessment and treatment using the SPE to preselect those suited to manual treatment of the neck. Part 2 (Main Feasibility Study) a mixed methods study will consist of a nested qualitative study examining service providers attitudes toward use of the SPE to identify individuals appropriate for neck rehabilitation following concussion (Orthopedic Manual Treatment (OMT) and neuromuscular/ sensorimotor retraining) and utility of this method in the context of current practice. Quantitative exploration of patient compliance, and satisfaction, as well as any adverse reactions to treatment will also contribute to determining overall feasibility of using the SPE. Part 3 (Experimental Study b.), a 3-month follow up will assess long-term effect of treatment selection based on use of the SPE. Combined evidence from these studies will be used to inform development of a future protocol for a pilot randomised, non-inferiority, controlled trial.

Study Procedure and Setting: Participants will take part in one screening session in the Laboratories located at the School of Physiotherapy, University of Otago, Dunedin (referred to as “*screening session*”). Participants identified as eligible to enter the treatment arm of the study will then be invited to participate in further treatment session (referred to as “*treating sessions*”) where they will attend 2 physiotherapy sessions per week for 4 weeks at physiotherapy clinics local to Dunedin. Follow-up assessment (referred to as “*follow up sessions*”) for participants entering the treatment arm of the study will then be conducted 1 week and 3 months following cessation of treatment and will take place at the University of

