Volunteers who: respond to advertisement i) using the online screening questionnaire relating to the inclusion/exclusion criteria (primarily whether they have sustained a medically diagnosed concussion within the last 14 days); ii) the study phone; iii) the study email, or who are referred by a health practitioner will be contacted by the study SC. The SC will further screen them for inclusion and exclusion criteria. If eligible to participate in the screening session participants will be forwarded an electronic participant information sheet and consent form and scheduled for the screening session. Individuals contacting the SC in response to advertising who meet exclusion criteria at any stage of the screening process will be provided with names and contact details of primary health services for concussion in Dunedin for follow up if desired. Those recruited via advertisement will be requested to obtain written confirmation of their concussion from their treating physician.

Inclusion criteria: Adults aged 18-60 years, biological sex: male, female, who have sustained a medically diagnosed concussion (mild Traumatic Brain Injury) based on published diagnostic criteria [13-15] and are not more than 14 days since injury [14].

Exclusion criteria: Individuals with past or current history of:

- Moderate to severe TBI as defined by published diagnostic criteria [16]
- Diagnosed concussion with associated trauma related abnormalities apparent on CT or MRI and/ or cervical spine fracture
- Diagnosed concussion due to assault
- Neck pain unrelated to concussion injury(/ies) (requiring treatment)
- Headache disorders (including cervicogenic, migraine (chronic), and tensions type headaches)
- Vestibular, oculomotor, neurological disorders
- Major psychiatric disorders currently being actively treated
- Physical injury that would prevent completion of the screening session

Study power:

Based on previously identified rates of neck impairment post-concussion [9, 17] it is anticipated that screening of **160** participants will be required to identify **60** individuals who meet inclusion criteria. Allowing for 50% of individuals to decline participation in the trial and a 10% drop-out rate, it is anticipated that data from **n=27** participants (treatment commenced with **n=30**) will be collected at all data collection time points. This group size is consistent with those currently used in randomised control trials investigating outcome following OMT of the

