Participants identified as eligible for allocation to the treatment arm of the study will be booked for their initial treatment session a maximum of 2 weeks following the screening session. Participants will be assessed during the first treatment session using an extended standardised assessment of the cervical spine (1 hour). Additional tests of musculoskeletal [31, 71] and sensorimotor function [72] as well as neural mechanosensitivity [73], standard to physiotherapy clinical practice in management of disorders of the neck and concussion [74], in addition to baseline results (provided in report form via post from the SC and supplied to the treating physiotherapist) will inform individualised treatment plans [18, 75]. Following initial assessment by the therapist, participants will receive treatment twice weekly for 4 weeks. During this time participants will also be requested to avoid alternate treatments for their concussion (except for use of prescribed medication/s) to minimise potential for confounding.

Interventions:

Treatment for management of identified neck impairments provided will include OMT (For e.g., Maitland, and Mulligan intervertebral joint mobilisation techniques) neuromuscular and sensorimotor retraining techniques standard to musculoskeletal physiotherapy practice internationally and in New Zealand for management of neck disorders [18, 75]. Individual treatment plans will be pragmatically determined. All participants receiving treatment will be provided with advice and education relating to graduated return to activity and prescribed a sub-symptom threshold cardiovascular exercise program using previously published

guidelines for exercise intensity dose [76]. This adjunct treatment aligns with internationally accepted standards of best practice for concussion management [4].

Treating physiotherapists, up-skilling, and treatment monitoring:

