Treating physiotherapists will be New Zealand registered, and hold current annual practicing certificates, Physiotherapy New Zealand membership, and ACC registration. They will hold additional training in OMT to at least diploma level with a minimum of 5 years clinical experience. Treating therapists will also participate in an initial 1 x 3 hour study induction session followed by 2 x 1 hour follow-up study review sessions (April to August). These sessions will be conducted by the PI (OG), a Masters (Musculoskeletal Physiotherapy) qualified physiotherapist, with 20+ years of clinical experience and expertise treating disorders of the neck including concussion, who is registered with the PNZ, and holds a current APC, and ACC registration. Sessions will provide physiotherapists treating patients in the study with an opportunity for continuing education related to concussion management. All sessions will be in person.

Follow up sessions:

Procedure:

Following completion of the treatment protocol all participants will be contacted by the SC and scheduled for follow-up review sessions (1 week and 3 months following completion of treatment sessions or if treatment sessions were not completed in full per-protocol follow up times). Follow-up sessions will be held at the same laboratories attended for the screening session. Participants will be requested to complete the same battery of questionnaires 1 day prior to attending each time and will also be examined using the SPE on both occasions. Participants will also be administered with activity monitors at each follow up and asked to wear these for a further 7 days and complete the daily activity and sleep logs. All participants completing these follow up sessions will be provided with a \$40 voucher to recognise the reasonable costs involved with participating in this study.

Nested Qualitative Focus Groups and Interviews:

Procedure:

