Linear mixed method analysis of repeated experimental outcomes will determine treatment effect. Effect modifiers including sex and age as well as statistically significant demographic confounders will be included in the final model. Further secondary analysis may be undertaken using data collected at all time points. Multivariable linear regression will identify items of the VOMS which best predict VNG OM.

Data storage:

All data (including patient and health practitioner data) will be stored on the personal password-protected laptops of the PI ([name]) and or the password-protected study laptop. Any hard copies of the questionnaires and consent forms will be stored in the PI's office in a secure filing cabinet. Only the researchers mentioned in the application and the SC (tba) responsible for processing and analysis will have access to the de-identified data collected during the study. The principal researcher ([name]) and the SC will keep a list identification codes with participant names, so that participants can be identified by their coded data if needed.

A standardised hard copy of the summary report of the participants findings from the screening session completed by the SC will be provided to the treating physiotherapist (via postal mail). This will not be de-identified since it will be used by the treating physiotherapist to inform treatment. A copy of these reports will be kept on the PI's personal password-protected laptop.

The treating physiotherapist will record the clinical assessment and treatments, as required, on their usual practice management systems as well as information related to study feasibility.

All data will be stored for the duration of the study on the primary investigator's password-protected University laptop and will be accessible by members of the research team. It will also be stored for at least 10 years in the school's archive folder on the High-Capacity Storage System (HCSS). Any personal information held about the participants (such as contact details and hard copy questionnaires) may be destroyed at completion of the research. Coded study information may be kept by the University of Otago in secure, cloud-based storage indefinitely. All storage will comply with NZ I data security guidelines.

Potential problems: (medical/legal; issues with disclosure; conflict of interest, etc)

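### The single-group design can estimate only within-participant change over time, yet the protocol calls that change a treatment effect and draws SPE accuracy and clinical efficacy from it

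*Protocol*

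**What the plan says.** - **Analysis** (Statistical Analysis, Objective 2): "Linear mixed method analysis of repeated experimental outcomes will determine treatment effect". Sex, age and significant demographic confounders enter the model.
- **Inference** (Study Objectives): response over time is to give preliminary evidence on the "efficacy of the simplified physical examination to accurately identify individuals who may be suited to physiotherapeutic intervention". The hypothesis paragraph adds that results will support feasibility "as well as the clinical efficacy of this approach for managing neck related signs and symptoms following concussion".
- **Design** (Study Design): Part 1 is described as "a single-group pretest-posttest clinical design will provide preliminary (pilot) evidence of combined effect of assessment and treatment". Part 3 is to assess the long-term effect of SPE-based treatment selection at 3 months. Follow-up is described only for those entering the treatment arm.
- **Baseline** (Inclusion criteria): participants "are not more than 14 days since injury". Background puts the share of concussed people who develop persistent symptoms at up to 30%.
- **Entry to treatment**: at least 3 positive neck tests and fewer than 2 positive vestibulo-ocular tests. Ineligible participants get return-to-activity information or referral.
- **Start of treatment** (Treatment sessions procedure): participants are "booked for their initial treatment session a maximum of 2 weeks following the screening session". Interventions adds activity advice and an aerobic programme for everyone treated.
- **Outcomes**: treated participants "will also be examined using the SPE on both occasions". Kinematics, flexor endurance, manual examination and joint position error serve both as entry tests and as experimental outcomes.

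**The concern.** A treatment effect is a contrast with what would have happened without treatment. This study observes no untreated course, and time on study moves together with time since injury. The baseline is taken in the acute phase, when spontaneous improvement is to be expected. The model's time coefficient therefore cannot separate recovery from treatment, whatever covariates are added.

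SPE accuracy is further out of reach. To say that the SPE picks out people suited to neck treatment, one must compare the benefit of treatment in SPE-positive and SPE-negative people. That comparison has four cells (positive or negative, treated or not), and the study observes one.

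At stake is the reading of Objective 2. Ordinary recovery could be published as efficacy and as validation of the screening examination, and that evidence is meant to inform a later randomised trial.

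**Working it through.** **1. The plan's own figure.** Study power: 160 screened, 60 eligible (60/160 = 37.5%). 60 × (1 − 0.50) = 30 start treatment. 30 × (1 − 0.10) = 27 have data at all time points. This reproduces exactly. No alpha, effect size or SD is given for Objective 2, so there is no power figure to reproduce.

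**2. Who has outcome data.** 160 − 60 = 100 ineligible and 60 − 30 = 30 declining participants have no planned follow-up. Up to 130 of 160 screened people therefore contribute nothing to a statement about SPE accuracy.

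**3. Time before treatment.** Screening to the 1-week follow-up is at most 14 + 28 + 7 = 49 days, of which up to 14 (14/49 = 29%) precede study treatment. From injury, that visit falls between about 28 + 7 = 35 days and 14 + 14 + 28 + 7 = 63 days. The extended assessment at the first treatment session informs the treatment plan but is not named as an outcome time point.

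**4. Chance of a significant change with no treatment effect.** The check uses a paired t-test as a simple stand-in for one mixed-model time contrast: n = 27, two-sided alpha 0.05 (assumed), critical t on 26 df = 2.056, noncentrality = d × √27, where d is natural change in SDs of the change score (assumed; the protocol gives none).

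| d | d × √27 | P(significant) |
|---|---|---|
| 0 | 0 | 5% |
| 0.2 | 1.04 | 17% |
| 0.3 | 1.56 | 32% |
| 0.5 | 2.60 | 71% |
| 0.8 | 4.16 | 98% |

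**5. Regression to the mean on the entry tests.** Simulation with no true change: six latent-normal tests, selection on at least 3 positive, 30–40% positive per test and inter-test correlation 0.2–0.4 (all assumed), reliability 0.68–0.85. The reliabilities come from the protocol (joint position error 0.68; flexor endurance 0.83 and 0.85). Results:
- The mean shift per test is about 0.03–0.10 SD, which at n = 27 is significant in about 6–10% of studies.
- About 17–36% of those selected have fewer than 3 positives on retest.

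A five-test variant selecting 37.5%, with reliability 0.68–0.90 and correlation 0–0.5, gives 0.03–0.12 SD and 16–41%. The protocol also quotes values outside the first range (kinematics mostly 0.84–0.93; manual examination 0.63–0.96), and higher reliability shrinks the shift.

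The NDI and HIT-6 are not entry tests, so this mechanism does not act on them directly. For the vestibulo-ocular tests, entry requires few positives, so it runs towards apparent worsening.

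**The case against.** The best defence is that the protocol knows what it is. It declares a feasibility study, its primary outcomes are feasibility outcomes, the outcome table is labelled exploratory, Objective 2 promises preliminary evidence, and Part 1 speaks of a combined effect. It never claims an effect of manual therapy alone, and the exercise and advice are openly described as adjunct treatment.

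Much of this stands. A single group suits feasibility, and the co-interventions are not hidden. But preliminary describes precision, whereas the problem here is identification: a larger single group would have the same fault. The analysis sentence itself carries no qualifier. Asking participants to avoid other treatments does not deal with time since injury.

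A reader might also infer more than the documents support:
- *That a significant result is close to guaranteed.* This holds only if natural change is about 0.8 SD or more, a size found nowhere in the protocol.
- *That about 19 of 27 (0.70 × 27 = 18.9) would recover anyway.* The 30% figure covers all concussions and a symptom status. It does not describe people selected for neck impairment, or change in NDI or physical tests, and it does not say that the others recovered without care.
- *That regression to the mean drives the result.* Per test it is small. The larger retest percentages concern the eligibility count, which is not a listed outcome.
- *That everyone has two untreated weeks.* Two weeks is a maximum, and the protocol does not say what other care may occur in that gap.
- *That the observed change will power the later trial.* Study Design says only that combined evidence will inform its development, and the Timeline mentions a grant submission using pilot outcome data.

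**Conclusion.** The point holds as a fault of inference and wording in Objective 2, its hypothesis and Part 3. The design estimates within-participant change. It cannot identify a treatment effect, clinical efficacy, a long-term effect of treatment selection, or the accuracy of the SPE. That conclusion follows from the design alone and rests on no assumed number.

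The size does rest on assumptions. With no treatment effect and 27 completers, the chance of a significant change runs from 17% to 98% as assumed natural change goes from 0.2 to 0.8 SD of change. Natural recovery is the main potential source of bias. Regression to the mean adds about 0.03–0.10 SD on entry tests under the stated assumptions. Feasibility Objective 1 and the VOMS-to-VNG prediction analysis do not depend on this inference.

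**What to change.** 1. **Statistical Analysis, Objective 2.** State that the mixed model *will estimate within-participant change over time, which cannot be attributed to treatment*.
2. **Study Objectives and Study Design.** Remove the inference from response over time to SPE accuracy, clinical efficacy and long-term treatment effect. Describe Parts 1 and 3 as change at 1 week and 3 months after treatment.
3. **Later trial.** State that the observed change will not be used as a treatment-effect estimate when that trial is designed. SD, within-person correlation and retention may be used.
4. **Cheap addition.** Repeat the NDI and RPQ at the first treatment session and use them as the pre-treatment baseline for those scores. Report the screening-to-first-session change descriptively, with its varying interval (0–14 days). The RPQ is in the questionnaire battery but must be added to the experimental outcome table.

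**Cost.** Items 1 to 3 are protocol wording and give a weaker headline claim. Item 4 adds a few minutes for about 30 people at a 1-hour assessment already planned; the protocol itself notes that questionnaires may temporarily raise symptoms.

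**Limits.** Item 4 does not remove natural recovery during the treatment weeks, and the physical tests stay on the screening baseline. It therefore does not replace items 1 to 3.

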Participants identified as eligible for entry to treatment arm: will include those participants who demonstrate positive findings for a minimum of 3 cervical spine musculoskeletal and or sensorimotor outcome [12] as well as an absence of 2 or more positive oculomotor indicators of vestibulo-ocular impairment [55, 57]

Participants identified as ineligible for entry to treatment arm: identified due to an absence of sufficient positive neck related physical assessment findings, or alternately a positive

vestibulo-ocular screen will be provided with standardised graduated return to activity information [14, 70] as well as appropriate referral where evidence of vestibulo-ocular or physiological impairment is identified by the SC.

Of note, the SC conducting the laboratory-based screening session will be a New Zealand registered physiotherapist, and hold a current annual practicing certificate, Physiotherapy New Zealand membership, and ACC registration. They will hold additional training in OMT with a minimum of 3 years clinical experience. They will also have received specialised training from the PI (OG) in assessments to be used during the screening session including performance of testing, data reduction, and analysis of quantifiable outcomes necessary to establish participant eligibility for enrolment in the treatment arm of the study.

Estimated duration of total testing time will be 1.25 hour (1 hour for the SPE and 0.25 hours for induction and consent). All participants who provide consent and complete the SPE will be provided with a \$40 voucher to recognise the reasonable costs involved with participating in this study.

Treatment Sessions:

Treatment sessions procedure:

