We will use Thematic Analysis, an evaluative deductive approach to analyse the qualitative focus group and interview data, as described by Clarke and Braun [77]. The SC will code each transcription and one of the researchers will code every third transcription, grouping the codes into themes and sub-themes. An iterative process will be used within the research team to define the main themes and emerging models related to the study aims. In this way thematic analysis will be reflexive to aid in identification of any instances where the PI's beliefs may unduly influence identification of these main themes.

Quantified feasibility outcomes: activity, compliance, and adverse event monitoring

Participants will record daily performance of home exercises prescribed by the treating therapist in an activity-log (yes/ no, minutes of exercise per day) to determine treatment compliance. Non-attendance at scheduled treatment sessions will be recorded by the treating therapist (yes/no per session) as well as any adverse reactions to treatment (number). Participants will complete an exiting questionnaire to assess patient satisfaction [78].

Experimental Outcomes:

Experimental outcome measures (experimental studies a. & b.) will include but are not limited to:

Category	Exploratory OM
Cervical Spine	

Kinematic Assessment - Virtual Reality	Total range of motion (deg) Peak Velocity – Rotation R (deg/s) Peak Velocity – Rotation L (deg/s) Peak Velocity – Rotation Ext. (deg/s) Global head motion accuracy (deg)
Muscle Function (CFET)	Total time (sec)
Manual Spinal Examination	Pos/ neg
Sensorimotor Function (JPE)	Degrees Error (deg) Neck Disability Index (tot/ 50) Headache Impact Test-6
Vestibulo-Ocular	
VNG OM Assessment	Full Assessment (≥ 2 pos/neg overall (pos/neg) ; pos/neg per assessment)
VOMS assessment	Increase in symptoms (11- point NRS) ; avg NPC > 5cm Dizziness Handicap Index
Participant Outcomes	
Physical Activity : Actigraphy	Minutes of Vigorous Physical Activity, min/day Physical Activity (TAC/d; steps/d; PAEE - kcal/kg/day) Activity log Consensus Sleep Diary PROMIS sleep questionnaires IPAQ (METs) Fatigue Severity Scale
Quality of Life	EuroQol-5D-5L (EQ VAS)

Data Management

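### The protocol promises to validate an oculomotor screen, but the only analysis it states selects the best VOMS items in the same participants, which is derivation, so accuracy reported from those data will on average be too high

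*Protocol*

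**What the plan says.** Protocol, Study Objectives, objective 2: "Included in this objective will be use of data to validate a clinical objective oculomotor screen to improve clinical utility of the SPE".

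Protocol, Statistical Analysis, Objective 2: "Multivariable linear regression will identify items of the VOMS which best predict VNG OM". This is the only analysis in the protocol that bears on an oculomotor screen.

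The Experimental Outcomes table gives the two sides of the model. VNG is recorded as "Full Assessment (≥ 2 pos/neg overall (pos/neg) ; pos/neg per assessment", and VOMS as "Increase in symptoms (11- point NRS) ; avg NPC > 5cm". The number of VOMS items to enter is not given.

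No sample size or accuracy target is attached to the VOMS analysis. Study power gives only the recruitment cascade, beginning "screening of 160 participants will be required to identify 60 individuals who meet inclusion criteria".

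**The concern.** The objective and the analysis do not match. Validation asks how well a fixed rule performs. The stated analysis looks for the rule. If its fit or accuracy is then reported from the same participants, the figure includes the benefit of having been tuned to them. This holds whether the model is linear or logistic.

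A weak relation between VOMS and VNG is a real possibility on the protocol's own account. The Vestibular Oculomotor Screen section says the tool was designed for ages 9 to 40, whereas the study enrols ages 18 to 60. The same section warns that VOMS symptoms may arise from the cervical spine, particularly where cervical sensorimotor tests are abnormal, and those are the patients the SPE is meant to find.

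The risk is that items chosen partly by chance are described as validated and carried into the future trial protocol that this study is meant to inform.

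**Working it through.** **1. The plan's own figures.** The cascade reproduces: 60 × (1 − 0.50) = 30 starting treatment, and 30 × (1 − 0.10) = 27 with complete data. Implied eligibility is 60/160 = 37.5%. Entry to treatment requires sufficient neck findings "as well as an absence of 2 or more positive oculomotor indicators of vestibulo-ocular impairment", so every treated participant is VNG-negative overall at baseline. Only the whole screened cohort contains both VNG results at baseline. That makes 160 the largest possible sample; the analysis set itself is not stated.

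**2. Chance that an unrelated item looks significant.** For k independent items tested at 0.05, P(at least one) = 1 − 0.95^k:
- k = 5: 22.6%
- k = 7: 30.2%
- k = 10: 40.1%

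With correlated items (0.6), 160 participants, 6 to 10 items and 20% to 50% VNG-positive, simulation of a multivariable linear model with no true association gives 24% to 39%.

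**3. Apparent discrimination when nothing is related.** The true AUC is 0.50. In the same settings the mean in-sample AUC is 0.61 to 0.67 with all items kept, and about 0.60 to 0.65 with only the three best kept.

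A second set of null simulations kept the three items with the smallest p-values, refitted the model, and scored the rule in the same data and in 3,000 new participants (inter-item correlation 0.5, 7 items):

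| Participants | VNG-positive | Apparent AUC | AUC in new participants |
|---|---|---|---|
| 160 | 30% | 0.62 | 0.50 |
| 160 | 15% | 0.65 | 0.50 |
| 100 | 30% | 0.65 | 0.50 |
| 60 | 30% | 0.69 | 0.50 |

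In the first row, with the cut-off that maximises sensitivity plus specificity, apparent sensitivity and specificity are 0.63 and 0.61. In new participants they are 0.47 and 0.54.

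**4. Apparent discrimination when one item is truly related** (latent correlation 0.4, 160 participants, 30% positive, three best kept):
- 7 items: apparent 0.716, new data 0.665, excess 0.716 − 0.665 = 0.051
- 14 items: apparent 0.720, new data 0.652, excess 0.720 − 0.652 = 0.068

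**5. Can the named method show no prediction?** Yes. In the null settings of step 3 (160 participants, 6 to 10 items), the overall F-test of the regression rejects in about 5% of studies (4% to 6% across settings), and mean adjusted R² is 0.00. The protocol does not say that items are selected only if this test supports prediction.

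The item count, VNG-positive share, inter-item correlation and number of items kept are not in the protocol. They are assumptions.

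**The case against.** **Selection thresholds and resampling belong in an SAP.** That is fair, and their absence is not the point here. An SAP could add a p-value filter or a bootstrap. The protocol would still promise validation while naming only a selection step, and that mismatch lies within this document.

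**The plan cannot fail.** A reader might infer that the rule always returns a screen and that no result could show VOMS to be uninformative. The text does not support this. It follows only if 'best' is taken as a bare ranking and all other regression output is ignored. The ranking reading has some support, because the same paragraph sets a significance criterion for demographic confounders and none for VOMS items. But the overall test in step 5 can show no prediction, and the protocol does not rule out using it.

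**The protocol names no AUC, sensitivity or specificity.** Correct. The figures above illustrate any in-sample accuracy that might be reported; they do not criticise a statistic the plan promises. An AUC of 0.60 to 0.67 would also not normally pass for a good screen.

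**'Validate' may mean criterion validity of an existing tool against a reference test.** That reading would answer the point if the whole VOMS, or items fixed in advance, were compared with VNG. The stated analysis selects items, so accuracy quoted for the selected subset is still optimistic.

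**The consequence is limited.** A reader might infer that the chosen items will replace VNG as the gate to neck treatment. No section says so: VNG itself decides entry in this study, and the objective speaks only of clinical utility. No current participant is affected. The work is also labelled preliminary and exploratory.

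**Conclusion.** The point holds as a mismatch between objective and analysis: the protocol says validate and describes derivation. Any accuracy reported for the selected items from the same data will be too high on average, though not in every dataset. With 160 participants and 6 to 10 items, the excess in AUC is about 0.10 to 0.17 if nothing is related (0.60 to 0.67 against 0.50). It is about 0.05 if one of 7 items is truly related. In the simulated settings it grows with fewer participants and with more items. These sizes rest on the assumptions listed, since the protocol fixes none of them apart from the 160.

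The documents do not support saying that the plan must always produce a screen, or that the items will become the entry gate. The analysis is secondary, but its stated claim goes beyond what the method can show, and the correction is cheap.

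**What to change.** 1. In objective 2, replace 'validate' with 'derive and internally validate'.
2. In Statistical Analysis, Objective 2, state that VOMS items are selected only if the overall model test supports prediction of VNG. Otherwise the report says that the data do not support a VOMS screen for VNG.
3. Repeat the whole selection step in each bootstrap sample. Optimism is the mean, over bootstrap samples, of a rule's performance in its own bootstrap sample minus its performance in the original data. Corrected performance is apparent performance minus optimism. Report corrected discrimination, sensitivity and specificity against overall VNG status, with 95% CIs.
4. State that external validation is still needed before the items are used in the SPE.

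No numerical accuracy bar for adoption is proposed, because the protocol gives no basis for one.

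The cost is a few sentences and a bootstrap on data already being collected. The small downside is that the reported accuracy will be lower than the uncorrected figure.
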